3.4 Participant selection

The study will recruit 54 trial participants, 18 per locality over a seven-month period. As this is a small feasibility study a statistical sample size calculation is not appropriate. Instead, sample size was a pragmatic decision, informed by guidance on feasibility trials [18,19]. Teresi et al. (2022) [19] state that sample sizes in feasibility studies should consider budget constraints; participant flow and numbers needed to answer the feasibility questions. Our primary objective for the trial is to assess the feasibility of the methods and processes for use in a larger study therefore a sample size of 54 was deemed achievable and would provide enough data to evaluate trial design including recruitment, retention, adherence, and acceptability of outcome measures.

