6.1.1 Criteria for progression to full RCT

Descriptive data on recruitment, retention, response rates and adherence to the course will be framed against the below, traffic-lit progression criteria:

	Participants	Action
Go (Green)	
a) Recruitment: ≥ 45 participants with dementia recruited in 7-month period (equates to $>83\%$ of desired sample of 54)
 
b) Retention: $\geq 75\%$ of recruited participants remain in the study (excluding deaths)
 
c) Data collection: $\geq 75\%$ provide data at each time point
 
d) Adherence: $\geq 75\%$ of intervention group adhere to the intervention
	Continue to full trial
Amend (Amber)	
a) Recruitment: 30 to 44 participants recruited
 
b) Retention: 50-74% remain in the study (excluding deaths)
 
c) Data collection: 50-74% provide data at each time point
 
d) Adherence: 50-74% adhere to the intervention
	Proceed with adaptations
Stop (Red)	
a) Recruitment: < 27 participants ($< 50\%$ of expected sample)
 
b) Retention: $< 50\%$ remain in the study (excluding deaths)
 
c) Data collection: $< 50\%$ provide data at each time point
 
d) Adherence: $< 50\%$ adhere to the intervention
	Consider not proceeding

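### The recruitment progression bands leave totals of 27, 28 and 29 unclassified, so the protocol gives no action for those results

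*Protocol*

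**What the plan says.** Section 3.4 of the protocol sets the target: "The study will recruit 54 trial participants, 18 per locality over a seven-month period". Section 6.1.1 then states how the results will be used: "Descriptive data on recruitment, retention, response rates and adherence to the course will be framed against the below, traffic-lit progression criteria".

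For recruitment, the three rows of that table read:

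- Green: "a) Recruitment: ≥ 45 participants with dementia recruited in 7-month period", which the table describes as more than 83% of the target
- Amber: "a) Recruitment: 30 to 44 participants recruited"
- Red: "a) Recruitment: < 27 participants", which the table describes as less than 50% of the expected sample

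The other three criteria (retention, data collection, adherence) are given as percentages. The Amber row for retention is typical: "b) Retention: 50-74% remain in the study (excluding deaths"). For all three, Green starts at 75% and Red is anything below 50%. The action attached to Green is to continue to the full trial, to Amber to go ahead after adapting the design, and to Red to consider not going ahead.

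**The concern.** A traffic-light rule is useful only if every attainable result has a colour fixed in advance. Here the Amber recruitment band stops at 30 on the way down and the Red band begins at 26, so the whole numbers between them have no colour and no action.

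Recruitment is among the primary objectives in section 2.2, and section 3.4 justifies the sample of 54 partly by its ability to evaluate recruitment. The table in section 6.1.1 is the only place where a recruitment total is linked to a progression category. The gap also sits at the lower boundary, where the category changes from adapting the trial to considering not running it. A team with 27 to 29 recruits would choose the category knowing the answer, which is what criteria fixed in advance are meant to prevent.

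**Working it through.** **Inputs.** Target 54 (section 3.4). Green at least 45, Amber 30 to 44, Red below 27 (section 6.1.1). Amber floor of 50% and Red below 50% for retention, data collection and adherence (section 6.1.1). Section 3.4 declines a formal calculation ("As this is a small feasibility study a statistical sample size calculation is not appropriate"), so no power, error rate or variance enters.

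**Step 1: reproduce the table's own percentages.**

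- Green: 45/54 = 83.3%, which agrees with the stated figure of more than 83%.
- Red: 27/54 = 50.0%, so below 27 is below 50%, as labelled. The largest Red total is 26, and 26/54 = 48.1%.

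Both stated percentages are correct.

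**Step 2: express the Amber band on the same scale.** 30/54 = 55.6% and 44/54 = 81.5%. The Amber ceiling meets Green (44, then 45). The Amber floor does not meet Red (30, then 26).

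**Step 3: assign every total from 0 to 54.**

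| Total recruited | Share of 54 | Band |
|---|---|---|
| 0 to 26 | up to 48.1% | Red |
| 27 | 50.0% | none |
| 28 | 51.9% | none |
| 29 | 53.7% | none |
| 30 to 44 | 55.6% to 81.5% | Amber |
| 45 to 54 | 83.3% to 100% | Green |

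Three of the 55 totals fall in no band. None falls in two.

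**Step 4: compare with the other criteria.** For the other three criteria, Amber starts at 50% and Red lies below 50%, so those bands meet. Half of 54 is 27, which is where the recruitment Red row also draws its line. The Amber floor of 30 is the only entry that departs from a 50% boundary, and the protocol gives no reason for it.

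**Step 5: check that the totals are attainable.** Section 3.4.1 plans 36 consents to contact per site, 3 × 36 = 108 in all, with half converting to give 54. If all 108 were obtained, totals of 27 to 29 would correspond to conversion of 27/108 = 25.0% to 29/108 = 26.9%, about half the planned rate.

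**Step 6: test the candidate repairs.** Amber 27 to 44 with Red below 27 puts every total from 0 to 54 in exactly one band. So does Amber 30 to 44 with Red below 30. The first keeps the under-50% label true. The second does not, because 30/54 = 55.6%.

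**The case against.** The strongest reply concerns weight, not correctness. Section 6.1.1 frames descriptive results against the bands and does not bind anyone to them. The Red action is only to consider not proceeding, and the Amber action also leaves room for judgement. Section 6.2 adds that qualitative findings will be considered alongside the quantitative data. No allocation, estimate or safety matter depends on the gap. All of this stands, and it lowers the severity. It does not supply a category for 27 to 29.

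A reader might infer three stronger things that the protocol does not support.

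- **That the percentage bands have an equally serious hole between 74% and 75%.** On unrounded proportions, 40/54 = 74.07%, 35/47 = 74.47% and 38/51 = 74.51% do fall between Amber and Green. But the bands are in whole percentages, and ordinary rounding gives every result a colour: the first two become 74% (Amber) and the third 75% (Green). At the planned intervention group of 36, no adherence result lies there at all (26/36 = 72.2%, 27/36 = 75.0%). A rounding convention is commonly left to an analysis plan, so this is only a wording point.
- **That the gap is likely to be hit.** If the total were Poisson, the chance of 27 to 29 would peak at about 22% with a mean of 28. That mean is an assumption placed at the centre of the gap, and no document gives it. With other assumed means the chance is 17% (mean 32), 9% (36), 3% (40), 0.6% (45) and 0.01% (54), and 16% (24) or 6% (20) on the low side.
- **That the Amber floor must be the slip.** Recruitment does not share the other criteria's scale throughout, since its Green cut is 83% and theirs is 75%. A floor of 30 could be deliberate and the Red cut the error. The under-50% label favours 27 but does not prove it.

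**Conclusion.** The point holds for the recruitment row. Totals of 27, 28 and 29 have no category, and the protocol states no action for them. This follows from the table alone and rests on no outside assumption. It should be fixed, but it is not critical: the criteria guide judgement, and the gap matters only if recruitment ends at about half of target. The table's own label and its other three criteria point to 27 as the intended boundary, without settling it.

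**What to change.** Make the recruitment bands exhaustive before the recruitment total is known, in one of two ways:

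- **Amber 27 to 44, Red below 27.** This is the repair most consistent with the under-50% label and with the other three criteria. Only the Amber floor changes.
- **Amber 30 to 44, Red below 30.** This applies if 30 was intended. The under-50% label must then be replaced, because 30 is 55.6% of 54.

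The sponsor should confirm which boundary is meant.

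As a minor wording change in the same edit, write the percentage bands as at least 75%, at least 50% but below 75%, and below 50%, applied to unrounded proportions, so that no rounding convention is needed.

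The cost is a small protocol amendment. Under section 8.1 it needs sponsor review, submission to the HRA and notice to the participating NHS sites. Section 3.4.1 schedules recruitment for January to July 2026. The protocol cannot show whether the change would still come before the total is known, so its date should be recorded.

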6.2 Qualitative data

Transcripts will be analysed inductively using Framework [24] to facilitate reflexive thematic analysis [25] grounded in lived experience. The 2-day residential analysis workshop will enable the research team to draw on the expertise of experts by experience and other study partners. The research associate will lead the initial coding and discuss initial interpretations with other members of the team to reduce the influence of any one person. This will begin the process of theme development which will be further developed in the analysis workshop. Analysis will be an iterative ongoing process throughout the interview/focus group period, with qualitative data collection and initial analysis occurring simultaneously. Findings will be considered alongside the quantitative data analysis to consider the acceptability and feasibility of the study processes.

7 END OF STUDY PROCEDURES

The end of the study is defined as the point when the last participant has completed their 6 months post baseline follow up or the last qualitative interview for the embedded qualitative element of the study is completed, whichever is the latter.

The CI will notify the REC of the end of the trial or if the trial ends prematurely (with reasons).

8 ETHICAL AND REGULATORY CONSIDERATIONS

8.1 Research Ethics Committee (REC) and other Regulatory review & reports

The study will be subject to appropriate REC and HRA approvals as it involves NHS sites. The trial will be conducted in accordance with the protocol and GCP guidance where applicable.

Amendments will be reviewed by the Sponsor to assess whether they are substantial or non-substantial. Amendments will be submitted to the HRA for consideration. Participating NHS sites will be notified of all amendments. An amendment history will be kept within the study master file.

8.2 Peer review

The proposal for this feasibility trial has been peer-reviewed through the NIHR peer review process including both expert and lay reviewers.

8.3 Patient & Public Involvement (PPI)

The project has a dedicated PPI lead who has a background as a mental health social worker and extensive experience in PPI work and already has established networks with SA community groups having worked with them on the previous research of the Good Life course. The PPI involvement includes the following elements: a three-strand stakeholder advisory network, public members with lived experience on the study steering committee, advisors with lived experience on the project management group, and co-produced analysis residential. We will report on our PPI activity and outcomes guided by GRIPP2 [26]. Public members on the project management group, and study steering committee will be reimbursed for their attendance at meetings in line with NIHR guidance. Public members contributing to the three-strand stakeholder network will be given vouchers for their contributions and the community organisations supporting them can also be reimbursed for their efforts in supporting involvement.

8.3.1 Three strand stakeholder advisory network

We will establish a flexible, multi-modal stakeholder advisory network combining meetings with other forms of communication including email, telephone, discussion at existing groups and digital platforms. Ongoing PPIE will run across three strands:

1. Practitioner: statutory, voluntary and private sector practitioners who work in dementia care or support in some context, recruited through our existing extensive networks and ongoing networking activities. Meetings will be three times a year but can change in line with need. There will additionally be a wider practitioner network of interested practitioners who would like to be kept updated of progress of research and opportunities for involvement.

2. Lived experience: will consist of a core group of people with lived experience of dementia who would like regular and ongoing involvement in the research. They will be recruited through networks such as DEEP, Curious Minds and Involvement at York as well as service contacts at feasibility trial sites. Target membership will be 8-12, recognising that involvement may be fluid and influenced by members' health and wellbeing. Meetings will be 3 times a year. Additionally, there will be a wider lived experience group comprising of

people with experience of dementia (either personally, family member, friend) who will be kept updated on the progress of the research but can drop in and out.

There will also be a separate unpaid carers sub-group with options for regular meetings or more informal involvement. Any meetings would be separate to the core lived experience group unless both groups requested partnership working.

3. A subgroup specifically designed to engage people from SA communities: made up of South Asian people with dementia, family carers and the community workers who support them, recruited through the groups we built relationships with for the initial study. Work with this sub-group will take place through existing structures (groups which are already meeting) within a framework of wider activities. Opportunities for more informal ad-hoc contributions as requested/desired in a variety of formats will be available. Network members can join the wider lived experience or practice networks, and a SA member of this network will attend the study's steering committee as an expert by experience. Additionally, there will be an optional SA practitioner group comprising of practitioners with specific knowledge/expertise in working with SA communities.

The network will be facilitated by our dedicated PPIE lead, ensuring the insights of each strand inform the others. The schedule for involvement will be responsive to the needs of the project but is expected to include: 1) input into manual and training development; 2) recruitment approaches; 3) data collection; 4) implications of findings.

[figure not shown]

Figure 2 Representation of interconnected network

8.3.2 Study steering committee

The study steering committee will consist of a range of members with a mix of skills and knowledge from backgrounds such as the Department for Health and Social Care, dementia advocacy organisations and members with lived experience. This group will have an independent chair and independent PPIE members and will meet twice a year for independent oversight and to support study impact.

8.3.3 Project management group

This group includes a range of stakeholders including co-applicants, delivery partners and site staff from the three recruitment sites as well as the core research team. Two members of this group are experts by experience and have been closely involved with this project from the start. They were team members on the co-produced GL realist evaluation, and they worked on the development of the proposal for the feasibility study. This group meets quarterly, with responsibility for overall study management and to ensure a collaborative approach throughout.

8.3.4 Analysis residential

There will be a two-day residential analysis workshop that will include the experts by experience on the project, co-applicants and other study partners. The research team have experience of having run a similar workshop for the previous project.

Data management and some initial analysis will take place prior to the residential to ensure that the information presented is in an accessible format to enable an inclusive analysis workshop.

8.4 Data protection, patient confidentiality and research data management

Personal data (names, contact details) will be stored securely on University of York's secure server and only members of the research team and research administration staff will have access to it. This data will be stored separately to any research data and will only be used to contact participants about the research, follow up visits, and dissemination of findings. The recruiting sites will provide the research team with consent to contact information for potential participants via a secure online platform. Personal information for participants who

decide not to take part or do not meet the inclusion criteria will be destroyed. All paper consent forms will be scanned and stored electronically away from any research data. The paper version will then be securely destroyed. Any paper documentation containing identifiable information waiting to be scanned and stored electronically will be stored in a locked cabinet in the CI's office behind a door only members of the research team have access to.

Information containing personal identifiable information will not be removed from the sites apart from when securely transferring data to the research team. Participant details will be anonymised in any publications or reports resulting from the study.

At the point of informed consent all participants will be given a unique study ID which will then be used on all study documentation.

Exception- Canterbury wellbeing scales completed during course sessions will initially be identifiable using participants' first names (with a family name initial if there are duplicate first names on a course). The Canterbury wellbeing scale does not ask for any personal information, other than how the person is feeling 'in the moment' (engaged, interested etc.) Completed measures will be securely stored in a locked cupboard by the professional facilitators during the intervention period. A member of the research team will collect them as soon as possible after the intervention has finished and transfer them to Qualtrics with the participants' unique study IDs. Paper copies will be shredded.

8.4.1 For all other quantitative data

The online platform Qualtrics will be used to complete the demographics, service use and outcomes questionnaires with participants. Each participant will be given a unique identifier and only the research team will have access to the 'key' to unlock which ID belongs to which participant. The researchers will use a University of York encrypted iPad to collect questionnaire responses. In the event of this being lost or stolen the University of York has the ability to remotely lock or wipe the iPad and questionnaires can be completed offline where connectivity is a problem.

Qualtrics can be accessed securely via the internet to manage the questionnaires.

8.4.2 For qualitative data

The qualitative interviews will be voice recorded using a University of York encrypted voice recorder and transferred as soon as possible onto the secure server. The recording will then be deleted from the voice recorder. Audio recordings will be transcribed by a University of York approved transcription service that has the necessary confidentiality agreements

signed. Audio recordings and transcripts will be labelled with a study ID number and stored securely in line with the University of York's data storage policies.

Anonymised quotes may be used in publications and presentations and anonymised data may be made available for secondary data analysis by the research team or other researcher researching a relevant topic upon request. This will only be for participants who have indicated their agreement to the ongoing use of their anonymous data on their consent forms.

At the end of the study, study data will be archived for 10 years in accordance with the University of York Research Data Management Policy

<https://www.york.ac.uk/about/departments/support-and-admin/information-services/information-policy/index/research-data-management-policy/>

Access to study data will be limited to relevant individuals of the research team and the CI will act as data custodian.

The University of York will be the owner of the copyrights and associated intellectual rights in the study data.

8.4.3 Informing GP

Participants with dementia taking part in the feasibility study will be asked to give permission for their GP to be informed of their participation in the research. This will form part of the informed consent process. GP details will be collected via a secure online platform as part of the baseline background questions. GP's will be sent a letter and copy of the participant information sheet informing them of their patient's participation in the research for their records.

8.4.4 Informing carer

Participants with dementia taking part in the study will be asked to give permission for a member of their family or close friend (who could be contacted in an emergency or act as a consultee if required) to be informed of their participation in the research. This will form part of the informed consent process. Carer details will be collected via a secure online platform as part of the baseline background questions. Carers will be sent a letter and copy of the participant information sheet informing them of the person they support's participation in the research.

8.5 Indemnity

The University of York will act as Sponsor for the study and provided legal liability insurance. Contained within the PIS's is a statement regarding indemnity.

8.6 Trial conduct

The protocol will be adhered to throughout the study period, any deviations from the protocol will be documented and reported to the CI and sponsor if required.

A serious breach of the protocol will be reported to the sponsor immediately who will determine the seriousness of the breach and whether the REC need informing.

The research team will maintain regular contact with the recruitment sites to address any issues as they arise. The delivery sites will have ongoing supervision throughout the set up and delivery of the intervention to support with any issues relating to the intervention.

The Trial Master File will document all processes and management of the feasibility study including any deviations from the protocol.

8.6.1 Trial monitoring, audit and inspection

The trial will be monitored in agreement with the sponsors policy, which is consistent with the UK Policy Framework for Health and Social Care Research. All trial documentation will be made available upon request for monitoring or auditing purposes by the sponsor, and authorising REC.

A Trial Monitoring Plan will be developed by the sponsor and agreed by the PMG and CI.

Typically monitoring is delegated to the research team and is likely to include:

- Consent processes (taken by appropriate person and documented correctly)
- Data collection is consistent and adheres to protocol
- Adverse events, protocol deviations procedures are being followed and documented correctly
- No key data missing
- Data is valid
- Review of recruitment rates, withdrawals and loss to follow ups.

